## 5.6. Cross-over design

In order to ensure that participants in the active control group have the opportunity to enroll in the intervention, a cross over period 2 is in place. Enrolled participants who complete the first period of the study will be offered the possibility to participate in a follow-up assessment to ascertain a maintenance effect. While the primary endpoint is at the completion of period 1 for all participants, an identical schedule of acquisition is implemented for period 2. Both groups are offered the opportunity to crossover into the other arm of the study (intervention to active control; active control to intervention). This follow-up will consist in a cross-over to the opposite study arm to which they were initially randomized. The study will include two periods of 4 weeks separated by a washout period of at least 6 weeks.

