### 3. Method

#### 3.1 Recruitment

##### 3.1.1 Initial Contact

Older adult participants will be recruited through the PREVENT-AD cohort as an optional sub-study, by reaching out to potentially eligible participants by phone and email. Screening procedures will involve verbally screening potential participants over the phone. A staff member doing the screening will begin with an overview of the HABS project. The screener will then obtain verbal consent (see telephone script). The telephone script will ask questions concerning inclusion and exclusion criteria. The total time to administer all screening questions is approximately 40 minutes. The telephone screen will also assess the level of physical activity via self-reported physical activity. If eligibility is verified, a date and time will be scheduled for a virtual meeting between the participant and a researcher where the formal study consent will be signed. Those individuals that are deemed ineligible from the screening call will have their forms kept in a separate file on REDCap. This information will be used to quantify how many were ineligible from the screening call and the reasons for ineligibility.

The criteria will be assessed by one of the listed study personnel. No special expertise is required to evaluate screening responses. If a participant requires exclusion due to information received during a session, they will be contacted via telephone or email and informed that they have been excluded from further study, nevertheless remaining part of the PREVENT-AD cohort. The reason provided for their exclusion will be brief and will include a statement such as, "Based on the data collected in your last session, we will not require any further testing. As indicated in the beginning, participation depends on several factors and not all participants qualify for the entire study."

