### **3.3 Exclusion Criteria**

- Current or previous formal diagnosis of a DSM-V Axis I or II disorder including Major Depression (not including postpartum depression or anxiety)
- History of major psychiatric illness including schizophrenia
- Current treatment for cancer – except non-melanoma skin cancer
- Neurological condition (MS, Parkinson's, Dementia, Stroke) or moderate to severe traumatic brain injury.
- Current alcohol or substance abuse
- Current treatment for congestive heart failure, angina, uncontrolled arrhythmia, DVT or other cardiovascular condition
- Myocardial infarction, coronary artery bypass grafting, angioplasty or other cardiac event in the six months before enrollment.
- Regular use of an assisted walking device or significant increase in pain when walking
- Use of any antipsychotic, anti-depressant, anti-anxiety, and ADD/ADHD medications, other than for sleep.
- Not fluent in English or French
- No regular access to a smartphone or computer with internet
- Involvement in conflicting research studies currently or recently

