### 4.2. Study design

The HABS study is a remote behavioural intervention that is conducted as a single-blinded randomized controlled trial. Recruited participants will be categorized as either high or low risk for Alzheimer's disease, in accordance with Aim 1 to determine the extent to which the behavioral intervention improves physical activity in at-risk older adults. Participant classification into high and low risk is based on their already known biomarker and cognitive status available from PREVENT-AD using a multimodal risk score. Note, that this does not involve collection of any new data and this data is not shared with participants as per the PREVENT-AD protocol. For participant classification into high risk, an individual's score is taken from a two-tier system of variables. The first tier involves variables where a positive result involves higher risk for Alzheimer's disease: Amyloid Tau Index (ATI)  $\leq 1$ , and p-tau in cerebrospinal fluid,  $\beta$ -Amyloid, and Total tau in PET, or APOE  $\epsilon 4/\epsilon 4$  or  $\epsilon 4/\epsilon 3$  status. A single positive value in any of these variables classifies the participant into the higher risk group. The second tier involves variables that independently are not sufficient for higher risk classification but together with a second variable might indicate higher risk: Overall cognitive performance (i.e., Repeatable Battery for the Assessment of Neuropsychological Status [RBANS]), episodic memory (i.e., Rey Auditory Verbal Learning Test [RAVLT]), hippocampal volume on MRI, APOE  $\epsilon 4/\epsilon 2$  status, Framingham Risk Score, and history of depression or consumption of psychotropic medication. Any combination of two variables from this tier classifies the participant into the higher risk group. Participants that are not classified into the higher risk group either because they had negative results to all risk variables or because they had a positive score to only one risk variable from the second tier, will be randomized into the low-risk group. We expect that approximately 50% of our participants will be in the high-risk group. We are using stratified randomization to ensure that each higher risk participant will be equally distributed across the intervention and control groups. The participants in each risk group are randomized to either a social motivation group (intervention) or control with a ratio of 1:1. The stratified randomization scheme is prepared by the Harvard Catalyst Biostatistical Group using a permuted block method with random blocks [16]. The randomization scheme will be uploaded in the REDCap randomization module. At the end of the first study period, participants will be offered to participate in a follow-up to ascertain maintenance which will consist of a cross-over into the alternative arm to which they initially were randomized. The study consists of two 4-week study periods with at least a 6-week washout period in between. This trial is registered on clinicaltrials.gov with an identifier NCT04315363. This study received ethical approval from Northeastern University Institutional Review Board (IRB).

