
**NOTE ON STUDY DESIGN AND SINGLE-BLINDING:** It is important to note that in order maintain the single-blind nature of the study, participants will not be specifically told that the daily messages are the study intervention. Therefore, the consent form will simply mention that some participants may receive motivational messages, but will not elaborate further.

Hence, in terms of the cross-over design, it will be described as a long-term follow up in the ICF in order to maintain the single-blind and not bias the participants. A debriefing session will be held at the end of period 1 to explain to the participants that the motivational messages were the intervention and they will be offered to cross-over into the opposite arm. See section 5.6 for more information regarding the cross-over.

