#### Exercise

There are several common risks associated with exercise participation including injury to muscles or joints, especially when initiating an exercise program after a period of being sedentary. Further, there is a minor risk of dehydration or heat exhaustion. More commonly, there is a risk of falling. Based on our considerable experience in walking and balance-based research assessments and interventions in adults, many of whom are much older than the cohort anticipated for enrollment into this study, we are confident that this risk is rare, meaning that it will occur in less than .001% (less than 1 out of 100000) of people in the otherwise healthy adults targeted for this study. This risk will be minimized as we are focusing on walking and reductions in sedentary behaviour rather than exercise training. Adverse or unstable cardiovascular or pulmonary response to exercise, including disorders of heart rhythm, heart attack, stroke, or sudden death will be minimized, because assessment of vital signs and history of heart disease are included in our screening procedures, and only those adults with satisfactory results as detailed in our eligibility criteria will be allowed to participate in experimental procedures for this study. As such, we anticipate that this risk is rare. According to American College of Sports Medicine (ACSM), guidelines published in 2000, the risk of myocardial infarction (MI) in symptomatic (categorized with males and females having ventricular arrhythmias) and asymptomatic (without any signs or symptoms indicative of ischemic heart disease) individuals during exercise is less than 0.04%. The risk of death in the same population is less than or equal to 0.01%, and the risk of needing hospitalization (including acute heart attack and/or serious arrhythmia) is less than or equal to 0.2%. The risk of cardiovascular complications occurring during exercise is rare (occurs in less than 1% of people). A retrospective survey by the YMCA revealed 1 death and 1 cardiac arrest per 2,897,057 and 2,253,267 person-hours. To minimize the risk, we are using a *non-exercise estimation of cardiorespiratory fitness* that requires BMI and heart rate measurement only.

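### Minor safety gap: the visible text lets participants into optional period 2 without re-asking the cardiac and cancer-treatment questions, at least about 10 to 11 weeks after T1

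*Protocol*

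**What the plan says.** **Screening.** Section 3.1.1 places the eligibility questions in the telephone screen: "The telephone script will ask questions concerning inclusion and exclusion criteria". Section 3.1.2 puts consent after that call. The further screen described under Research Activities, between consent and randomization, covers anxiety, depression and cognitive impairment only.

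**Criteria that can change with time.** Section 3.3 excludes "Current treatment for congestive heart failure, angina, uncontrolled arrhythmia, DVT or other cardiovascular condition". It also excludes people under current treatment for cancer (other than non-melanoma skin cancer) and anyone with "Myocardial infarction, coronary artery bypass grafting, angioplasty or other cardiac event in the six months before enrollment".

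**The safeguard.** Section 9 (Exercise) says cardiovascular risk will be kept low because "assessment of vital signs and history of heart disease are included in our screening procedures" and because "only those adults with satisfactory results as detailed in our eligibility criteria will be allowed to participate in experimental procedures for this study".

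**Period 2.** Section 4.2 states: "The study consists of two 4-week study periods with at least a 6-week washout period in between". The note on blinding in that section adds: "A debriefing session will be held at the end of period 1". At that session participants are offered the opposite arm. Section 5.6 (Cross-over design) gives the entry condition: "Enrolled participants who complete the first period of the study will be offered the possibility to participate in a follow-up assessment". It also says that the period-1 acquisition schedule is repeated in period 2. The SAP does not discuss period 2.

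**The concern.** The section 9 safeguard works by asking about heart history and admitting only those who meet the criteria. For period 1 the text says when this is asked. For period 2 it does not, although period 2 is itself an experimental procedure under the protocol: the participant takes the opposite arm and repeats the assessments, including the walking, sit-to-stand and balance tests at T1.

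Two features make the screen go out of date. The treatment criteria refer to current treatment, which can start at any time. The cardiac-event window is tied to enrollment, so read literally it never covers an event after enrollment. Following the text as written, staff would admit to period 2 someone who had had a cardiac event since enrollment and did not mention it. That person would do the physical tests before any scheduled question about heart health.

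At stake is a small, avoidable exposure. Controls who cross over gain daily activity feedback and partner messages for reaching goals (section 5.3), and donations tied to activity goals (section 3.8.3.d). These are incentives to move more. Participants who cross from intervention to control gain no such incentive, so the concern is smaller for them.

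**Working it through.** The documents state no figure for the age of the screen at period 2, so there is none to reproduce. The check adds up the stated intervals and then applies an assumed event rate.

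**Timing inputs**
- T1 is 1 week before messaging starts (section 5.1).
- Each period lasts 4 weeks (sections 4.2 and 5.6).
- Washout is at least 6 weeks, with no maximum (sections 4.2 and 5.6).
- The interval from telephone screen to T1 is not stated.

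**Minimum time from T1 to the period-2 baseline**
- Baseline after the washout: 1 + 4 + 6 = 11 weeks.
- Baseline in the last washout week: 1 + 4 + 6 − 1 = 10 weeks.
- The cross-over offer comes at the end of period 1, which is 1 + 4 = 5 weeks after T1. So 11 − 5 = 6 weeks, or 10 − 5 = 5 weeks, fall after the offer.

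The telephone screen precedes T1, so 10 to 11 weeks is a lower bound on its age.

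**Expected number newly meeting a cardiac or cancer-treatment criterion**

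Formula: number crossing × weeks/52 × yearly rate. The rate is an assumption, taken as 1% to 5% per year. Full uptake of the optional period is also assumed. The protocol plans 120 participants randomized 1:1, so 60 controls; the SAP plans 30 controls.

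| Crossing controls | Low end (10 weeks, 1%) | High end (11 weeks, 5%) |
|---|---|---|
| 60 (protocol) | 60 × 10/52 × 0.01 = 0.12 | 60 × 11/52 × 0.05 = 0.63 |
| 30 (SAP) | 30 × 10/52 × 0.01 = 0.06 | 30 × 11/52 × 0.05 = 0.32 |

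**Sensitivity, 60 controls**
- Rate of 10% per year: 60 × 10/52 × 0.10 = 1.15 to 60 × 11/52 × 0.10 = 1.27.
- Only the weeks after the offer: 60 × 5/52 × 0.01 = 0.06 to 60 × 6/52 × 0.05 = 0.35.
- Longer washout: at 5% per year the expected number reaches one when the interval is 52/(60 × 0.05) = 17.3 weeks, about 6 weeks beyond the 11-week minimum.
- Only undisclosed cases fall in the gap. If half are disclosed, the main range halves to 0.06 to 0.32.

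These figures count people who would meet a criterion, not people harmed.

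**What else in the text could catch such a case**
- Section 3.1.1 lets staff exclude on information received in a session. It is not limited to period 1, but nothing prompts for the information.
- Under the repeated schedule, resting heart rate would be taken again (sections 5.4 and 5.5). It is self-reported and does not ask about history or treatment.
- The T1 physical tests (section 5.5) would probably show a mobility problem, but not a recent cardiac event or a new treatment.
- The post-consent screen, if repeated, covers mood and cognition only.

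None of these asks about a new cardiac event, or about new cardiac or cancer treatment.

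**The case against.** The strongest reply is that this rests on silence in an incomplete copy. Figure 1, the timeline document, the telephone script and the attached questionnaire spreadsheet are where a period-2 health check would naturally sit, and none can be read here. That stands: a re-check cannot be excluded, and the point is limited to the visible text.

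A second reply is that section 9 promises screening at entry, and that nobody is re-questioned during period 1 either. This stands in part. But period 2 is a separate, optional entry into the other arm after a washout with no upper limit, and section 9 refers to experimental procedures for the study as a whole.

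A third reply is that there is more contact than the main schedule suggests. Section 5.4 can be read as placing a fitness estimate four weeks after the intervention (section 5.5 words it differently), and section 5.5 names a T4 assessment whose timing the text does not give. Participants hold study contact details, and an independent safety officer receives biannual reports. These are real opportunities to learn of an event, but all depend on the participant raising it.

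A fourth reply is that the hazard is low. That stands in full. Section 4.1 says participants are not explicitly told to exercise, section 9 puts the focus on walking and less sitting, and Aim 1 already gives the comparator health messaging and home-based training.

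A reader might infer that period 2 runs without safeguards, or that staff could not stop an ineligible participant. The documents do not support this: the exclusion provisions in sections 3.1.1 and 3.2 apply throughout, and the sessions are repeated. Nor do they support an inference that participants are likely to be harmed.

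**Conclusion.** The point holds as a minor safety improvement. The visible text admits participants to period 2 on completing period 1, schedules no repeat of the cardiac and cancer-treatment questions, and anchors the six-month cardiac window to enrollment. The section 9 safeguard is therefore not actively checked for period 2.

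The size is small. At minimum timing, full uptake and an assumed 1% to 5% per year, fewer than one crossing control is expected to be affected, before allowing for disclosure. The rate is an assumption, and a higher rate or a much longer washout could bring the figure to about one. The conclusion also depends on no re-check existing in the documents missing from this copy. It does not touch the period-1 primary endpoint, the randomization or the sample size.

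**What to change.** Add to section 5.6 (Cross-over design):

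> At first contact for period 2, before any physical assessment, existing staff re-ask the cardiac and cancer-treatment questions of section 3.3, with the six-month cardiac window counted back from period-2 entry. A participant who meets one of these criteria does not undergo the period-2 physical tests or the period-2 intervention, but may still provide the crossover-baseline accelerometry and questionnaires for the maintenance analysis.

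Report the number affected by original arm. If one of the missing documents already contains this check, state it in 5.6 instead.

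The last clause of the proposed text matters because Aim 1 assesses maintenance at the crossover baseline. Barring people before that point would lose the measurement for no safety gain.

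The cost is a few sentences of protocol text and a few minutes of existing staff time per participant, using part of a script whose full version takes about 40 minutes. Across both arms, under the same assumptions, 120 × 10/52 × 0.01 = 0.23 to 120 × 11/52 × 0.05 = 1.27 people would meet a criterion. The period-2 intervention phase might therefore lose about one participant.

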## 5.6. Study partner

The study partner (grandchild, child or friend) of the main participant will undergo a shorter cognitive battery and questionnaires. The timeline for the study partner's participation is provided in Figure 3. Their participation will involve two main sessions T1s (pre) and T2s (post). Each session will take between 1.5-2 hours. During the 4-week intervention, each day if they reach their physical activity goal, the main participants will receive self-transcendence messages from a pre-set list of messages composed at the consent session with the study partner. The study partners will receive feedback on their relative's accelerometer performance.

Study partner's participation is limited to the study period where the main participant is taking part in the intervention arm. This means the study partner will only be involved in one of the study periods. If the main participant starts with the intervention arm, the study partner will only be part of study period 1 (Figure 1), and end its participation before the washout period. If the main participant starts in the control arm, the study partner's role will start after the washout period, i.e. during study period 2, when the main participant crosses over to the intervention arm.

**Figure 3.** Timeline study participants (Intervention Arm in Periods 1 and 2).

#### 6a. Data management

All research data are coded and only the research coordinator has access to identifiable information stored in a secure location. Data are stored electronically on password-protected servers behind university-protected firewalls. Data collected are stored in one of three ways; (1) MRI data (including tasks) and physical activity monitoring data are extracted from their respective software packages and uploaded directly to a secure data storage environment at a high-performance computing facility. (2) All pen-and-paper psychosocial and neuropsychological assessments are scored and uploaded to REDCap [28]. Computerized psychosocial assessments are collected directly in REDCap and computerized neuropsychological assessments are uploaded to REDCap [29]. The oTree library is used to distribute the daily intervention messages and collect survey data. This system runs on a Heroku server, a cloud-based system that sends and receives hash-encrypted links. Collected anonymized data are stored on the messaging site behind an administrative login on the Heroku server.

#### 6b Data analysis

Outcome measures outside of the neuropsychological assessment battery are as follows:

Outcome measure	Type	Timeframe	Brief description
Total step count (average steps/day)	Primary	Week 0 (baseline); Week 2; Week 4.	This metric quantifies the change in the average number of steps taken each day, from the baseline, Week 2, and Week 4. It is a marker of change in habitual ambulatory activity.
Sedentary behavior (average min/day)	Primary	Week 0 (baseline); Week 2; Week 4.	This metric quantifies the change in the average amount of time spent sedentary each day, from the baseline, Week 2, and Week 4.

			2, and Week 4. It is a marker of time spent inactive.
Moderate-vigorous activity (average min/day)	Secondary	Week 0 (baseline); Week 2; Week 4.	This metric quantifies the change in the average amount of time spent engaged in moderate-to-vigorous physical activity each day, from the baseline, Week 2, and Week 4. It is a marker of physical activity.
Walking Cadence	Secondary	Week 0 (baseline); Week 2; Week 4	This metric reflects the participant's average steps per minute. We will examine change from baseline over the course of the intervention.
Walking Bouts	Secondary	Week 0 (baseline); Week 2; Week 4	This measures the number of 'bouts' of physical activity (in our case, steps). We will have two counts: the number of 5+ minute bouts and the number of 10+ minute bouts of walking. We will examine changes from baseline over the course of the intervention.

A spreadsheet holding the list of neuropsychological assessments to be used, with brief descriptions, is attached. They will be administered at T1 (Week 0), T2 (Week 1), and T3 (Week 4).

To test our main hypothesis that social motivation + self-transcendence messaging + home-based physical training will produce the largest increase in physical activity over the course of the 4-week intervention compared to the active control, we will perform repeated measures ANCOVAs (with group as a between-subject factor and pre-post session as a within-subject factor). This hypothesis will be examined by analyzing total number of steps and percent time sedentary. We will analyze structural/functional MRI connectivity to test the hypothesis that increased physical activity following the intervention is associated with enhanced brain connectivity between brain regions in reward valuation (i.e., ventral tegmental area and ventral striatum) and social processing (vmPFC). We will conduct seed-based functional connectivity analyses using methods as in our prior research [9, 29-31]. To mitigate the influence of motion, we will identify and address artifactual motion outliers in data modeling, and employ quality assurance software to mitigate head motion artifacts and physiological aliasing ([https://www.nitrc.org/projects/artifact\\_detect](https://www.nitrc.org/projects/artifact_detect)). We will control for the effects of demographic variables (e.g., age, sex, education, diet, mood, socioeconomic status, alcohol, vascular risk factors and sleep). We apply a whole-brain height threshold of  $p < 0.001$  ( $T = 3.24$ ) and false discovery rate cluster threshold of  $p < 0.05$ . We will examine brain modularity, which indexes the segregation between networks, and has previously been shown to predict cognitive gains after a physical exercise intervention [20]. In addition to these hypothesis-driven analyses, we will perform an agnostic, data driven multi-voxel pattern analysis of resting-state data using an approach published by our collaborator [21].

After compiling all data across the 3 different data servers, data will be checked for completeness and correctness using frequency distributions (for missing data and out-of-range A-B values). Group differences at baseline are examined for variables including demographic factors (i.e., age, sex, educational level, socioeconomic status, culture), baseline sedentary time, self-report sitting time, and estimated fitness, in order to detect potential confounding factors. For the primary hypothesis that social motivation + self-transcendence messages decrease sedentary time more than an active control, all outcome measures about sedentary behaviour are first quantified using available software. Changes in sedentary behaviour (% daily sitting and lying time, minutes/per day in physical activity, count of steps) over time (3-time points) are analyzed using linear mixed effect models to account for the correlated data and likely heterogeneous variability.

Non-linear changes across 3-time points are also examined by including quadratic effects. These models will include a random intercept and slope to account for subject-specific changes as well as a group (2) x time (3) interaction fixed effect. This allows for modelling of the effect of our intervention as a function of both groups and time as well as accounting for potentially confounding covariates. All model assumptions will be tested both visually and formally and associations between covariates will be assessed to protect against multicollinearity.

Analyses on the resting state and task-based fMRI analyses are considered secondary. Briefly they will be modeled using the general linear model approach. First-level analyses will include all necessary nuisance regressors to minimize motion artifacts influence, spatial smoothing kernel and high pass filtering, as well as physiological aliasing for the low-frequency fluctuations in resting state data. To answer questions about the intervention effect and prediction of behavioural change, both a priori ROI seed-based analyses of functional connectivity are performed as well as data-driven whole-brain multi-voxel pattern analysis, modularity analyses and graph theory per several previous publications using data-driven approaches to predict clinical outcomes. Besides the primary outcomes, adherence and drop-outs are also included in the prediction model as outcome variables, to examine what individual characteristics affect participation in the current intervention. Robust-prediction models of MRI data and psychosocial measures will be generated using cross-validation methods to improve the generalization of the results.

Selection bias will also be considered in our study by comparing characteristics between the source population (i.e., PREVENT-AD participants) and the study sample. For eligible participants invited to participate in the study, we will document the proportion of those who decline and agree to participate. We will compare demographic information (age, sex, education, ethnicity, socioeconomic status, smoking status, and self-reported physical activity) between those who agree and those who refuse to participate using t-tests and chi-square tests of independence. Multivariate logistic regression models will be used to determine whether these characteristics are associated with acceptance relative to refusal to participate in the study.

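### The documents conflict on which endpoint and contrast form the primary test, and nothing settles the conflict or shares the SAP's single two-sided 0.05 between two outcomes typed Primary

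*Protocol*

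**What the plan says.** **Endpoint.** The outcome table in Protocol 6b has two rows typed Primary: "Total step count (average steps/day" and "Sedentary behavior (average min/day". A third row, "Moderate-vigorous activity (average min/day", is typed Secondary. The next paragraph carries the main hypothesis to two measures: "This hypothesis will be examined by analyzing total number of steps and percent time sedentary". The following paragraph opens differently: "For the primary hypothesis that social motivation + self-transcendence messages decrease sedentary time more than an active control". It then lists the measures to be analysed: "Changes in sedentary behaviour (% daily sitting and lying time, minutes/per day in physical activity, count of steps) over time (3-time points". Section 4.1 (Overview) names decreased sedentary behaviour as the primary measure. The Executive Summary, section 2 (Aim 1) and Aim 1 of the SAP call the primary outcome physical activity and choose no metric.

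**Unit.** Sedentary time is minutes per day in the table, a percentage of time in the next paragraph, and a percentage of daily sitting and lying time in the one after.

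**Model and contrast.** One paragraph of 6b says "we will perform repeated measures ANCOVAs (with group as a between-subject factor and pre-post session as a within-subject factor". The next plans a linear mixed model with a group by three-level time interaction, and also examines quadratic effects. The SAP names linear mixed models only. The Executive Summary describes change after the intervention against a pre-intervention baseline, and section 5.6 (Cross-over design) puts the primary endpoint at the completion of period 1.

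**Error rate.** The SAP gives one difference (10.0%), one standard deviation (14.0%), 80% power and one two-sided 0.05, and does not say which endpoint these describe. The only multiplicity control in either document is for imaging, a "false discovery rate cluster threshold of" 0.05.

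**The concern.** Section 2 calls the study a pilot, but its Aim 1 is to determine efficacy, and the SAP sizes the trial for a two-sided test at 0.05. That level means something only once the success rule is fixed. Suppose steps reach significance and sedentary time does not, or the reverse. Under the present text the trial could be reported as a success or as a failure, and both readings could cite section 6b. The same applies to the contrast: the pre-post comparison, the overall interaction and a quadratic term can disagree. A rule chosen after unblinded results are seen would carry little weight, so it needs to be settled beforehand.

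**Working it through.** **1. Reproduce the SAP's sample size.** Inputs: difference 10, SD 14, two-sided 0.05, 80% power (SAP, Statistical Design and Power).

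n per arm = 2 × (1.96 + 0.8416)² × 14² / 10² = 2 × 7.849 × 1.96 = 30.8, so 31 per arm (62 in total). The SAP has 30 per arm. At 30 per arm, power is 79.0% by the normal approximation and 77.6% by the t-test. The SAP's size therefore corresponds to one two-sided test at the full 0.05, with no allowance for a second endpoint.

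**2. False-positive rate if either labelled primary counts.** The rate is P(|Z1| > 1.96 or |Z2| > 1.96) for a bivariate normal pair with correlation r. If the endpoints were independent it would be 1 − 0.95² = 9.75%. The documents do not give r, so a range is shown.

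| r (absolute value) | Either significant | Both significant |
|---|---|---|
| 0 | 9.75% | 0.25% |
| 0.5 | 9.1% | 0.9% |
| 0.7 | 8.35% | 1.65% |
| 0.9 | 7.0% | 3.0% |
| 0.95 | 6.5% | 3.5% |

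The two columns sum to 10%, because P(either) = 0.05 + 0.05 − P(both). Independence is unlikely, since both measures come from the same people in the same wear weeks.

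**3. If both are required.** When neither effect is real, the rate is the last column. When only one is real, a false claim still needs the null endpoint to be significant, so the rate cannot exceed 5%. The cost is power. Assumptions: two-sample t-tests on change, the SAP's 10 and 14 applying to each endpoint's change, no dropout. Results are from 200,000 simulated trials per setting.

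| Per arm | One endpoint at 0.05 | Both required, r = 0.5 / 0.7 / 0.9 |
|---|---|---|
| 30 (SAP) | 77.6% | 65.5 / 68.3 / 72.2% |
| 60 (Protocol's 120 at 1:1) | 97.3% | 95.0 / 95.4 / 96.1% |

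At 30 per arm, 80 − 77.6 = 2.4 points of the gap to 80% belong to the SAP's own calculation, not to multiplicity.

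**4. Can the text supply the rule?**
- *Endpoint:* section 4.1 and the opening of the mixed-model paragraph favour sedentary time. The two Primary labels and the ANCOVA paragraph treat steps as its equal, and the mixed-model paragraph also lists steps. The Executive Summary, section 2 and the SAP do not choose.
- *Contrast:* the Executive Summary, section 5.6 and the pre-post ANCOVA point to change from baseline to the end of period 1. The group by time (3) interaction competes with that contrast.
- *Either or both, and alpha:* nothing in either document.

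**The case against.** The strongest reply is that the plan is less open than it looks. Section 4.1 names sedentary behaviour in the singular, the primary hypothesis is worded on sedentary time, section 5.6 fixes the time point, the ANCOVA paragraph has a pre-post contrast, and the SAP restricts the model to mixed models. This stands in part. A reader who inferred that the documents are silent on endpoint and contrast would be wrong: they speak several times and disagree. But none of these statements withdraws the Primary label from steps, and none says how two primaries are to be judged.

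A reader might also take 7–9% as the trial's error rate. The documents do not support that. It needs a rule that either outcome suffices, which no passage states, and a correlation of about 0.5–0.9, which no passage gives. Analysing steps and sedentary time could equally mean that both must succeed, and then 0.05 is kept.

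Nor does the list of three measures justify a rate for any of three succeeding, since no such rule is written. The differing units of sedentary time may be close to rescalings under 24-hour wear, so they need reconciling but do not in themselves add a test.

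The power figures are open to challenge too. The SAP does not say what its 14% describes, and it plans covariate-adjusted mixed models, not t-tests. They show the scale of the loss and do not predict the power of the planned analysis.

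The pilot label limits how much is claimed from the result, but does not remove the need for a rule where an efficacy test at 0.05 has been sized.

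**Conclusion.** The concern holds as an unreconciled conflict. Two outcomes are typed Primary, both serve the main hypothesis, the two analysis paragraphs differ in measures, unit and model, and the SAP's one 0.05 is not allocated.

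The size depends on the missing rule. If either counts, the false-positive rate lies above 5% and is at most 9.75%; the value within that range depends on the assumed correlation. If both are required, there is no inflation, but power falls to about 66–72% at 30 per arm, against 77.6% for one endpoint. At 60 per arm the loss is small: 95–96% against 97.3%. The power figures rest on t-tests on change, the SAP's 10% and 14% holding for each endpoint's change, and no dropout.

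Confidence is high that the rule is missing and moderate for the percentages. This should be settled before any unblinded analysis.

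**What to change.** Amend the SAP and Protocol 6b together.

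1. Name one primary endpoint with one unit. The choice is the sponsor's: section 4.1 and the mixed-model paragraph favour sedentary time, while the Executive Summary, section 2, the ANCOVA paragraph and the SAP speak of physical activity.
2. Define the primary test as the group difference in change from baseline to Week 4 of period 1, from the SAP's linear mixed model with time as three levels, at two-sided 0.05.
3. Test the other endpoint at 0.05 only if the first is significant. Alternatively, keep both as primary with Holm.
4. Make the Week 2 contrast, the overall group by time test and the repeated-measures ANCOVA supportive or sensitivity analyses. Drop the separate quadratic terms, because three-level time already contains them.
5. State that the minutes in physical activity listed in the mixed-model paragraph are not primary.

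Suggested SAP text: *The primary test is the group difference in change from baseline to Week 4 of period 1 in [endpoint, unit], from the linear mixed model, at two-sided 0.05. [Second endpoint] is tested at 0.05 only if this is significant. All other tests are supportive.*

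**Cost.** Wording only, with no new data. Under the assumptions above:
- *Fixed order:* the SAP's sample-size calculation is unchanged, but one listed primary becomes second in line. The chance of claiming it is 65–72% at 30 per arm (95–96% at 60) if both effects are real, but only about 3% (about 4–5% at 60) if it alone is real.
- *Holm:* per-endpoint power at 30 per arm is about 68% if only one effect is real and 72–74% if both are. At 60 per arm it is about 95% and 96–97%.
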